## 10. Data Collection and Statistical Analysis

This study is a formative evaluation to assess the implementation of a program that uses state-of-the-art tools and techniques (e.g. streamlined patient set-up, multi-channel education through coaching, and high-quality, patient-friendly devices) to engage patients in an educational program for CGM-based diabetes management. To do this, we will collect data to measure the degree to which each of the program elements has been effective.

As an evaluation study, the study is not hypothesis-driven, and involves no statistical analysis plan for hypothesis-testing. Further, as participation will be based on self-selection with no group assignment; there is no sample size calculation. Rather, this study is exploratory in nature.

In this study we anticipate enrolling 100 patients with T2D. Since our primary aim is to perform a formative evaluation of a new program, we plan to collect measures relevant to enrollment and device distribution processes, telephone and secure text messaging with study participants, and any challenges encountered (by both study participants and administrators) in the implementation of the program. We view these measures as benchmarks that will inform future program iterations and quality improvement efforts. We will also investigate whether the program may be more effective for certain subgroups; for example, whether observed differences in program adoption, persistence, behavior change, or changes in diabetes management markers (e.g., estimated glucose values and hemoglobin A1C measurements), vary according to such factors as age, familiarity with technology, educational attainment, or disease progression.

### Data Collection

Since our program achieves its efficacy through education, self-discovery, and the behavior change that results from that education, we will collect data about our ability to connect with and engage participants in the program. Specifically, we will collect data on recruitment efforts (e.g., recruitment rate; patient preferences in setting up their devices (i.e., via self-start or group visit); information related to study enrollment (e.g., method of enrollment, pre-program survey); and program engagement metrics (e.g., device calibrations, use of companion mobile application, CGM component completion

rates). By enrolling in the study, participants consent to the acquisition, review, and analysis of data from their medical records. We will also collect the following data, which will allow us to both evaluate the program as delivered, and to help us tailor future versions of the program to better serve the participants that we enroll:

- Reasons for declining to participate, as given to program personnel at different contact points
- Recordings of coaching calls and introductory training sessions
- Observations from coaches about the most effective calling procedures, behavioral strategies, talking points, and online facilitation techniques
- Time dedicated to device preparation, and to each aspect of the introductory training session
- Total letters sent, and the number returned due to bad addresses
- Recruitment strategies to which each potential participant was exposed
- Total coaching calls attempted and completed per participant, and the durations of those calls
- Suggestions made during coaching calls and during the exit interview about how to improve the program
- Demographic information such as age, education, and social support
- Survey results to assess familiarity with technology such as computers and smartphones, knowledge about nutrition and self-care, and self-efficacy in disease management.

A secondary goal is to evaluate the effectiveness of the program as implemented in this study. On all patients we will collect interstitial glucose levels from the CGM device, activity and other available data from the activity tracking device, blood glucose levels following CGM use, any changes in prescription medication use during the study, routine lab measures including A1Cs, any changes in mental health (specifically depression), and total costs of medical care before, during, and after the study. Patients will be asked to share their medical records and claims costs through February 28, 2028, even if patients stop using devices prior to February 28, 2018.

The following measurements will be collected from study participants:

Data Elements from Participants	Source	Data Collection Time				Post-Study 2/28/18-28
		Study Enrollment	During course of CGM	CGM Completion (10 weeks)	Study Completion (2/28/18)	
Age	Medical Record 	X				
Time since diabetes diagnosis	Enrollment Survey 	X				
Race/Ethnicity	Enrollment Survey 	X				
Hemoglobin A1C	Medical Record	X		X (90 days)	X (180 days)	X
Fasting blood glucose levels	Log or Coaching platform 			Daily through end of study	X	
Daily basal insulin dose	Log or Coaching platform 		Daily through end of study	Daily through end of study	X	
Diabetes Distress Questionnaire	Enrollment Survey 	X				
Cancer Indicator	Medical Record 	X				
Heart Failure Indicator	Medical Record 	X				

Diabetes medication indicator	Medical Record 	X		X		X
Metformin indicator	Medical Record 	X		X		X
Glipzide indicator	Medical Record 	X		X		X
Pioglitazone indicator	Medical Record 	X		X		X
Rosiglitazone indicator	Medical Record 	X		X		X
Sitagliptin indicator	Medical Record 	X		X		X
Linagliptin indicator	Medical Record 	X		X		X
Saxagliptin indicator	Medical Record 	X		X		X
Exenatide indicator	Medical Record 	X		X		X
Liraglutide indicator	Medical Record 	X		X		X
Glyburide indicator	Medical Record 	X		X		X
Basal insulin indicator	Medical Record 	X		X		X
Bolus insulin indicator	Medical Record 	X		X		X
Other prescription drug use	Medical Record 	X		X		X
Interstitial glucose levels	CGM device 		X	X		
Contacts with program coaches	Coaching platform 		X	X		X
Interactions with secure texting	Digital app 		X	X		X
Accelerometer data, including daily steps, distance walked, calories burned, active minutes, hourly activity, walking goal achievement, stationary time; heart rate; sleep stages, duration, and consistency; and any other metrics as available.	Activity tracking device 		X	X		X
Total cost of medical care during program	Medical Record 					X
WHO-5 Well-Being Index (depression screen)	Pre/post study surveys	X				X
Exit Interview Questionnaire	Post-study survey 					X
Additional information from medical record and/or claims costs as needed		X	X	X	X	X

These items will be abstracted from the patient's medical record or administrative claims by Savvysherpa research staff

This survey will be mailed to participants or delivered over the phone by a coach or call agents.

Dexcom will securely transfer CGM-based EGV measurements to Savvysherpa.

"Coaching platform" refers to any interactions with human coaches via phone or the study app.

Savvysherpa will collect patients' use of text messaging.

Savvysherpa will collect data from activity trackers via participants syncing their activity tracking devices.

Savvysherpa researchers will identify this from participants' administrative medical claims.

This survey will be mailed to participants or delivered over the phone by a coach or call agents.

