The patient will then be sent a consent packet that contains a cover letter from the program, a program brochure, a copy of the program eligibility criteria, two copies of the consent and authorization form (one to sign and return and one to keep), an information sheet on CGM, a Fitbit sizing guide, and a program survey.

If a patient is invited to study during a clinic visit and wishes to learn more, the patient may also meet and discuss the study with the clinical research coordinator (CRC), and receive a consent packet at that time.

---

 Inclusion/exclusion criteria have been determined by [name] and [name], Co-Investigators and Senior Medical Directors at SMA.

COMPLETION	
 
Patient completes survey.
 
Patient keeps the smartphone and tracker if patient has continued to track and sync steps through end of study period.
 

EDUCATION	
 
Patient wears CGM system for 10 weeks.
 
Patient is encouraged to wear activity tracker throughout end of study.
 
Throughout the study, patient will receive a weekly call from patient's coach.
 
Coach will be available to patient via phone and text through duration of study.
 
Patient may request CGM summary data to-date at any time during study.
 

SET-UP	
 
Patients have option to start using CGM on their own at home or at a group visit at the study site. If needed the CRC will assist patients with set-up at home.
 
Patients choosing home set-up on their own will receive devices in the mail. Patients choosing the group visit will receive devices during the visit.
 
During and after CGM initial set-up, the patient will have access to the CGM system Quick Start Guide, instructional videos, instructional booklet, and guidance from Dexcom technical support, program staff, the CRC, and/or a coach.
 
Patients will receive activity tracker instruction and support from coach when patients feel they are ready to start tracking activity.
 

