CONSENT	
After receiving packet, patient is encouraged to call program rep with any questions.
 
Patient is provided with web links to view device terms and conditions, privacy policies, and activity tracker safety information. CGM safety information is provided in the consent form.
 
Patient provides consent in one of two ways:
 
 
Via mail – patient mails in study copy of signed form
 
In person – patient gives signed form to on-site CRC
 

INVITATION	
 
Qualifying patients receive two recruitment letters and are also invited to the study during clinic visits.
 
Patients are asked to contact program rep for more information via phone message &/or website form.
 
When requested, or if no response to one or more letters, rep calls patient.
 
Program rep provides program info, determines patient interest in program, and sends consent packet to patient.
 
Following an in-clinic invitation, patients may elect to meet with CRC on site to receive packet and further study information.
 
 
Consent packet includes cover letter, program brochure, CGM info sheet, eligibility criteria sheet, patient and study copies of the consent form, Fitbit size guide, and program survey.

Figure 2. Type 2 diabetes CGM study stages

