#### [CGM-based education and coaching](#)

This part of the study will be implemented by coaches who have undergone diabetes management training that incorporates device information, educational content, and techniques based on behavioral discussion and patient self-learning/empowerment. Coaches will also be equipped to help patients use

activity data in conjunction with their CGM use. Coaches will receive training regarding human research subjects to insure the ethical treatment and safety of all participants. All training will be reinforced during contact with study staff.

The information contained in the Standard of Care document has been approved by the study's Medical Directors (co-investigators) as providing fundamental diabetes self-management information to patients with T2D. In the Standard of Care document, patients are instructed that this information does not replace individual guidance given to patients from their providers.

Each participant will be assigned a coach who will provide education and support via phone and secure text messaging throughout the course of the study. Education will be centered around the four educational objectives (food intake and PPG, walking to reduce PPG, medication adherence, and nighttime glucose monitoring) and reinforcement of messages in the patient standard of care document. The coach will provide education on how to optimally use the CGM system for self-discovery, focusing on effective times to look at the CGM and behaviors that are likely to impact the CGM (outlined above). Coaches will assist participants in setting personalized goals and act as a sounding board for participants to discuss their self-discoveries. Coaches will review with patients the Rule of 15 to deal with hypoglycemic episodes.

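### A coach, including the participant's own, may deliver the exit questionnaire by phone, and no delivery route is stated for the WHO-5

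*Protocol*

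**What the plan says.** The table of data elements in section 10 (Data Collection) lists an Exit Interview Questionnaire whose source is the post-study survey. Footnote 8 sets its delivery: "This survey will be mailed to participants or delivered over the phone by a coach or call agents". Footnote 2, attached to the enrollment survey, has the same wording.

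The WHO-5 is marked at enrollment and post-study. Its source is given as "Pre/post study surveys", with no footnote.

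On the coach, section 6 (CGM-based education and coaching) states: "Each participant will be assigned a coach who will provide education and support via phone and secure text messaging throughout the course of the study". Section 6 (Program Length) continues the weekly coaching calls after the ten weeks of CGM, through February 28, 2018.

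On the paper route at the start, section 6 (Recruitment) describes a consent packet that includes "an information sheet on CGM, a Fitbit sizing guide, and a program survey". Figure 2 lists the same packet contents.

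On use of the data, section 10 collects "Suggestions made during coaching calls and during the exit interview about how to improve the program". It names participant surveys among the inputs to the qualitative formative evaluation, and lists change in depression among the data gathered for the secondary effectiveness goal.

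**The concern.** The primary aim is to learn how well the program is delivered, and coaching is one of its main components. If a coach collects the exit feedback, the person asking is someone whose work is being judged. A participant who has had weekly calls with that coach may not say that the calls were unhelpful, too frequent or badly timed. Those are the comments that a formative evaluation most needs.

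The exit survey matters more because much of the other qualitative material already passes through coaches: their notes, their observations, and suggestions made to them during calls. The exit survey is one of the few channels that could reach the evaluators without a coach in between.

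For the WHO-5 the risk is different. It is repeated, so a change in survey mode or interviewer between the two times adds to the observed change. With no comparison group, that part cannot be separated from change under the program.

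**Working it through.** No figure in the protocol depends on survey delivery, so there is nothing to reproduce. The check sets the table rows and footnotes side by side.

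| Instrument | When | Source in table | Footnote | Routes allowed |
|---|---|---|---|---|
| Exit Interview Questionnaire | Post-study | Post-study survey | 8 | Mail; phone by coach; phone by call agent |
| Enrollment survey items (such as diabetes distress) | Enrollment | Enrollment survey | 2 | The same three |
| WHO-5 | Enrollment and post-study | Pre/post study surveys | None | Not stated |

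**1. Exit questionnaire.** Footnote 8 names a coach without restriction. Each participant has an assigned coach to the end of the study, and no text bars that coach from this task. Delivery by the participant's own coach is therefore permitted, though not required.

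**2. WHO-5.** The row has no footnote, so coach delivery is neither stated nor excluded. If the WHO-5 travels with the enrollment and post-study surveys, as its source entry suggests, three routes are open at each time. That gives 3 × 3 = 9 combinations within a participant. The route is the same at both times in 3 of them and differs in 9 − 3 = 6. Mail before and coach after is 1 of the 9.

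**3. Same route, different relationship.** Even with a coach at both times, the conditions are not equal. At enrollment there is little or no relationship with the coach. At study end there have been weekly calls.

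**4. Size.** Let p0 and p1 be the shares of WHO-5 forms taken by a coach at enrollment and post-study. Let d0 and d1 be the mean shifts in score that coach administration causes at those times. The bias in the mean change is

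B = p1 × d1 − p0 × d0.

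The protocol gives none of the four. It does not split mail from phone, or coach from call agent. B is zero if the two products are equal, and its sign depends on which is larger. Step 3 is a reason to expect d1 to exceed d0, but that is a judgement and not a figure in the document.

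**5. Reach.** The A1C comes from the medical record and interstitial glucose from the CGM device. Neither passes through a survey.

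**The case against.** The strongest case against is that footnote 8 only permits coach delivery. It offers mail and call agents as well, and does not name the participant's own coach. The study is an exploratory pilot of 100 people with no hypothesis test, and it deliberately uses coaches as a source of feedback. A familiar coach may also get more replies. The WHO-5 is not among the endpoints named under Program effectiveness, although that list is expressly open-ended.

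Most of this stands, and it limits the priority of the point. It does not remove it. The existing use of coaches for feedback is a reason to keep one channel free of them. Who administers a survey is also a collection rule that this protocol fixes itself, and no later analysis can recover criticism that was never voiced.

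Two stronger readings go too far:

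- A reader might infer that the baseline survey is done on paper and the final one by the coach, so that mode and assessor change together in the program's favour. The packet does contain a program survey, and paper is a real route at the start. But the packet text does not call it the enrollment survey, and footnote 2 allows a coach or call agent to deliver the enrollment survey by phone. The pattern is possible, not specified.
- A reader might also say that ratings of the program are biased. The protocol describes suggestions for improvement and mentions no rating items or satisfaction score.

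**Conclusion.** The point holds in a limited form. The protocol lets a coach, including the assigned one, collect exit feedback that feeds the primary formative evaluation. It leaves the WHO-5 route unstated, so post-study collection of that scale could be affected too. Mode and administrator are open at both times and may differ within a participant.

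The size cannot be stated. A reader might assume that half the post-study forms are taken by a coach, that this raises the score by 5 to 10 points, and that no baseline form is affected. That would give 0.5 × 5 = 2.5 to 0.5 × 10 = 5 points. Every input would be invented, and the last one sets aside footnote 2. The figure should not be used.

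The conclusion rests on one behavioural assumption: that some participants are less candid with a coach than on paper or with a stranger. The A1C and CGM endpoints are unaffected. This is a cheap improvement, not a flaw that threatens the study.

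**What to change.** - In footnote 8, remove the coach as a delivery route for the Exit Interview Questionnaire. Use mail first, then call agents who have not coached that participant for those who do not reply.
- Add a footnote to the WHO-5 row that states this same route at enrollment and at study end, with the same mode at both times for each participant where possible.
- Record the mode and the type of administrator for each survey.

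The cost is a change to one footnote, one new footnote and two recorded items. Mail and call agents are already in the protocol, so no new resource is needed. The downside is that response may be slightly lower than when the familiar coach asks.

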## Statistical Analysis

### Formative evaluation

During and after the study, we will conduct a qualitative assessment to evaluate the implementation of the proposed diabetes self-management program. Qualitative information to be analyzed will include coaches notes, descriptions of requests for technical support, observations of nurse visits, and information provided through participant surveys. The purpose of this study is to generate insights that will inform a future, larger study evaluating the effectiveness of the program across a larger study population. While we will measure many of the same outcomes in that future study, the design and implementation will evolve based on the results of the current study. We intend to conduct multivariate analyses to evaluate program implementation performance in various subgroups; for example, we will evaluate enrollment rates, program completion rates, and other participation metrics against participant demographics and disease progression measures. This analysis will be carried out using intent-to-treat analysis principles.

### Program effectiveness

While it is not the primary aim of this study, the data we collect will be used to evaluate the program's effectiveness in maintaining participants' glycemic control. We will evaluate changes in participants' A1C measurements over time, as well as summary statistics of interstitial glucose measurements obtained from CGM devices, similar to those examined by Lind et al. (Lind, 2017). Endpoints of interest to this analysis include but are not limited to average measured glucose levels over the course of the study, glucose variability, changes in medication, and frequency and nature of medical care utilization throughout the study timeframe. This analysis will provide insight into patients' ability to self-manage their glucose levels using the program, as well as help refine the program and inform the design of a future, larger study of its effectiveness.

All eligible participants will be included in the analysis.

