## Consent

To ensure that patients' eligibility is consistent with information present in their medical records, patients will be asked in the consent form to review the eligibility criteria and confirm that they meet them before signing the form.

To assure informed consent, prospective patients will be given at least two days to review the consent form and the opportunity to talk with a program representative who has been trained in human subjects research. Patients with any medical concerns that they feel may affect their participation will be referred to their providers.

Patients will also be provided with manufacturer resource phone numbers should they have any specific device-related questions. For the CGM system, they will have access to a dedicated patient care and technical support line exclusively for patients in this study. The consent form itself will contain safety information related to study devices. Patients will also receive web links to the CGM system and activity tracker terms and conditions and privacy policies that they may view prior to providing consent. We will ask patients to review and agree to these terms prior to receiving their devices so that patient accounts can be created for the smartphone apps, thus reducing the set-up burden for the participant. Once participants receive their devices, this link will also be accessible on the smartphones for reference.

Patients who receive a consent packet in the mail will be able to provide consent either by signing a paper copy and returning it in the mail or bringing it to the study site. Prior to providing consent, patients will have the opportunity to talk with a program representative to discuss any questions or concerns the patient may have.

Patients receiving a consent packet on site from the CRC will have the opportunity to discuss any study-related questions or concerns with the CRC, and the option of consenting to the study at that time.

Patients will not receive devices prior to completing the informed consent.

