## **7. Selection and Withdrawal of Subjects**

Study participants will be recruited from the Machuca Family Medicine patient census. To be eligible for the program, patients must meet specific inclusion/exclusion criteria. The criteria selects in particular for patients who struggle the most in managing their diabetes, as indicated by their diabetes medication(s). All patients who meet the selection criteria will be invited to participate in the program regardless of their latest A1C test.

---

 The Fitbit may also record and display distance walked, calories burned, active minutes, hourly activity, stationary time, heart rate, and sleep stages, duration, and consistency; and contain tools to help users meet their personal health and fitness goals.

We intend to enroll 100 program participants (defined as those to whom program materials and devices have been delivered). When 100 participants have been enrolled, any patients that have been recruited but who have not yet been enrolled (including those who may have signed a consent form) may choose to be notified of any other upcoming study opportunities for which they may be eligible.

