### Exclusion Criteria

Patients will not be eligible if any of the following criteria pertain to them:

- Pregnant
- Blind
- Deaf
- Currently receiving chemotherapy or radiation therapy to treat cancer
- Addicted to any drugs (including alcohol, painkillers, hallucinogens, or others)
- Critically ill
- Diagnosed with or experiencing:
  - Kidney disease stages 4 and 5
  - End stage renal disease
  - Severe liver disease
  - Dementia
  - Schizophrenia
  - Bipolar disorder
  - Autism
  - An intellectual or learning disability
  - Arrhythmias other than atrial fibrillation
  - Congestive heart failure
- Has had a:
  - Myocardial infarction within the last 6 months
  - Stroke within the last 6 months
  - Stroke that resulted in significant disability (e.g., unable to write clearly or walk)

To ensure the medical records used to select patients accurately reflect the patient's current health status, patients will confirm their eligibility by reviewing the criteria provided in the consent packet and the consent form, and attesting to their eligibility by signing the consent form.

If during the study a patient's status changes such that s/he is no longer eligible to participate (with the exception of medication changes), the patient will be removed from the study. At that time the patient

will be asked to return all devices (with the exception of used sensors, the used transmitter, and the glucometer if the patient received one).

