### Patient Participation

All program participants will participate at-will and have the freedom to terminate their participation at any time. Participants, including those who intend to withdraw from the program or those who have withdrawn will be able to access program coaches for assistance with any program-related questions or issues.

Coaches will schedule weekly calls with participating patients. If patients demonstrate by their actions that they no longer want to participate in the study by no longer syncing their CGM or activity tracker data, outbound call or text messaging efforts will be made to reach the patient. If after three weeks there has been no data received and no communication with the patient, a voicemail will be left asking patients to reply within three days or they will be considered dropped from the study. No response to these voicemails will result in the shipment to these patients of a postage-paid box and a letter. The letter will inform patients that they are considered as non-participating and need to return the CGM devices, activity tracker, and smartphone.

During the course of the program, should any participant report medical issues that may affect that patient's ability to participate in the program, the patient will be directed to consult with the study doctor.

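### Does the effectiveness analysis leave out participants who lose eligibility through a new illness during the study?

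*Protocol*

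**What the plan says.** The protocol's Program effectiveness subsection (section 10) states: "All eligible participants will be included in the analysis". It gives no time point for the word eligible. Among the endpoints it names is how often, and for what, participants use medical care during the study.

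The protocol uses the idea of eligibility in two ways:

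- **At entry.** Under Consent (section 6), "patients will be asked in the consent form to review the eligibility criteria and confirm that they meet them before signing the form". The Exclusion Criteria (section 7) repeat that the signature attests to eligibility.
- **During the study.** The same Exclusion Criteria say that if a patient's status changes so that he or she "is no longer eligible to participate (with the exception of medication changes), the patient will be removed from the study". The patient is then asked to return devices.

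Participants are defined at the start of section 7: "We intend to enroll 100 program participants (defined as those to whom program materials and devices have been delivered". On data, section 10 (Data Collection) says: "By enrolling in the study, participants consent to the acquisition, review, and analysis of data from their medical records". Collection under the secondary goal is universal: "On all patients we will collect interstitial glucose levels from the CGM device", and the same list includes "total costs of medical care before, during, and after the study". Records and claims are requested even from people who stop using the devices early.

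The intent-to-treat principle is stated once, at the end of the Formative evaluation subsection, and is not repeated under Program effectiveness.

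**The concern.** Since participants are already defined by device delivery and have attested to eligibility, the adjective eligible seems to add little unless it means something more, such as still eligible. The removal rule uses the word in just that sense.

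Under that reading the analysis would select on its own outcome. Eight of the listed criteria are illnesses or treatments that generate care themselves: chemotherapy or radiation, critical illness, advanced kidney disease, severe liver disease, arrhythmia, congestive heart failure, myocardial infarction and stroke. Leaving out the people who have such events would understate utilization and cost. The reading could also be settled after the events are known, and these estimates are meant to help design a larger study. The intent-to-treat sentence stands under a different heading, so it does not plainly close the question.

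**Working it through.** The protocol gives no power, effect size or sample-size figure on this point, so there is nothing of its own to reproduce. The check has two parts.

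**1. Which reading does the text support?**

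- Sections 6 and 7 use eligible almost throughout for selection: who is identified from records, who is invited, who may receive a device, who confirms the criteria before signing.
- The one contrary use, in the removal rule, is about continuing in the program. Apart from removal, its only stated consequence is device return. It says nothing about deleting data or leaving people out of an analysis.
- Patient Participation (section 7) keeps the label after people leave: "Participants, including those who intend to withdraw from the program or those who have withdrawn" can still reach a coach. Leaving the program therefore does not end participant status.
- Data Collection covers all patients for the secondary goal and rests on consent given by enrolling.
- Under the entry reading the adjective still has work to do: it screens out anyone enrolled in error. The protocol recognises that risk by having patients check a selection made from medical records.

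**2. How large could the effect be under the other reading?**

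Inputs: N = 100 (section 7). The number removed, k, and their utilization relative to the others, R, are assumptions; the documents give neither. Set the others' mean utilization to 1.

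Mean in everyone = (100 + k(R − 1))/100. Mean without the removed = 1. Understatement:

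u = k(R − 1) / (100 + k(R − 1)), so k(R − 1) = 100u/(1 − u).

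- u = 10%: k(R − 1) = 10/0.90 = 11.11
- u = 5%: k(R − 1) = 5/0.95 = 5.26

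| Removed, k | R needed for 5% | R needed for 10% |
|---|---|---|
| 2 | 3.63 | 6.56 |
| 3 | 2.75 | 4.70 |
| 5 | 2.05 | 3.22 |

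Read in the other direction:

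- 1 removed at R = 3: 2/102 = 2.0%
- 3 removed at R = 5: 12/112 = 10.7%
- 5 removed at R = 10: 45/145 = 31.0%

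At R = 1 there is no bias.

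For mean A1C change the shift is (k/100) × d, where d is the assumed difference between removed and other participants:

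- k = 1, d = 0.5: 0.005 points
- k = 3, d = 1.0: 0.030 points
- k = 5, d = 1.0: 0.050 points

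The utilization formula assumes that removed participants have data for the whole period. If their follow-up is cut short at removal, part of their care is unobserved whichever reading is used.

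**The case for a change.** The best case for a change is that the protocol does more than stay silent. It fixes the analysis set with a word that it elsewhere uses for a status that can be lost. The data-collection statements govern what is gathered rather than who is analysed, and they do not mention people removed for lost eligibility. The protocol also says it has no statistical analysis plan for hypothesis testing, so this sentence may carry more weight than usual. A short phrase would settle it.

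Part of this stands. The sentence names no time point, the intent-to-treat statement does not formally reach it, and a few removals with very high use of care could move a mean utilization figure by more than 10%.

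It does not make the plan wrong. The two provisions do not contradict each other: one governs participation, the other analysis. No statement excludes a removed participant, and the surrounding text points towards keeping them. The time point for membership of an analysis set is commonly defined in a SAP. The disclaimer covers only hypothesis testing, so a descriptive plan may exist. Concern about choosing the reading afterwards has little force where there is one group, no test and no decision rule, and the endpoint list is openly not exhaustive.

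**Conclusion.** The concern does not call for a change. The sentence leaves a definition unwritten, and the ordinary reading, eligibility judged at entry, is sound: later illness then removes nobody from the analysis and the bias is zero.

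Harm would need two things together: the less natural still-eligible reading, and enough removals with much higher use of care. The second rests wholly on assumed inputs: below k(R − 1) of about 5.3 the understatement stays under 5%, and 10% needs about 11.1. For A1C, the main glycemic measure, the shift is 0.005 to 0.05 points with 1 to 5 removals and differences of 0.5 to 1.0 points. Removal can happen only during the study, so events in the record follow-up from 2018 to 2028 cannot trigger it. Cost is collected but is not named among the endpoints in the Program effectiveness subsection.

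The estimates affected are descriptive, secondary and exploratory. The conclusion assumes that analysts take eligible in the sense the protocol mostly uses, and that consent covers the records of removed participants. The consent pages are not available to confirm the latter.
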